15.2 Power Analysis: For the power analysis for the primary analyses, we calculated the minimum detectable effect size (MDES) assuming  $n = 200$ ,  $\alpha = .05$ , and power = .80 with 12 covariates in our model. Power was estimated in R (R Core Team) using the pwr library (Champely, 2018). A power analysis was performed to quantify the minimum detectable effect size ( $f^2$ ) for a three-way interaction between social buffering condition, sex, and pubertal stage within a multiple regression model controlling for the 12 covariates, all two-way interactions, and the main effects (the most complex model considered in our primary analysis, see Equation 1 below). Assuming these conditions, we should be able to detect an  $f^2$  of 0.056. In

other words, adding the three-way interaction to a model containing the covariates and all lower order interactions and main effects, the three-way interaction would need to explain an additional 5.6% of the variability to be detected. This falls between Cohen's criteria for a small ( $f^2 = .02$ ) and medium effect ( $f^2 = .15$ ) (Cohen, 1988). With a sample size of 200, even if we lose 40 of the participants to movement artifact for the imaging analyses, assuming all the previous conditions but a sample size of 160, we will still have an  $f^2$  of .070, or still within a small-medium effect size. As the number of covariates decreases, the size of the MDSE will decrease. Therefore, this represents a conservative estimate of the power for our primary analyses as we are likely to have fewer covariates in our models and will use multiple imputation to correct for missing data. For the two-way interaction and main effects models, described below, the power will be larger than these reported values as the models will be simpler.

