### 15.3 Statistical Analysis of MRI and non-MRI Outcome Variables:

The following is a list of the analyses that we will perform on the outcome measures. They are classified as to whether they are the primary or mediational analyses. All statistical analyses will be performed in R.

The primary analyses will consist of a series of multiple regression models. For each dependent variable, variation in neural activity, cortisol response, and heart rate response, we will begin by testing the three-way interaction between social buffering condition, sex, and pubertal stage for all outcomes. If the three-way interaction is not significant, we will then examine all two-way interactions. If the two-way interactions are not significant, we will then examine main effects only models. If the three-way interaction is significant, we will not examine any other model. If condition is significant as an interaction or as a main effect, we will examine all pairwise comparisons using Tukey's Honestly Significant Difference test.

Multiplicity of testing. We will correct for multiple comparisons using the Benjamini-Hochberg (BH) correction. The BH method works by controlling the false discovery rate, and relative to the Bonferroni's correction is more powerful, while still adequately protecting against Type I error (Williams, Jones, & Tukey, 1999).

Mediational Analysis. When changes in activity of brain regions differ by condition or condition by pubertal status and we also see condition or condition by pubertal status differences for cortisol, or heart rate, then we will examine whether brain activity differences mediate the neuroendocrine or autonomic differences. This will be examined using path analysis, while controlling for covariates identified in the preliminary

covariate analysis, and will be estimated using the lavaan package in R (Rosseel, 2012).

The significance of all indirect effects will be assessed using bias-corrected 95% confidence intervals (Efron & Tibshirani, 1986), where confidence intervals that are non-overlapping with zero will be considered significant.

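### Section 15.2 says the two-way and main-effect tests have more power than reported; that holds for each model tested alone, but not for the stepwise procedure in Section 15.3

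*Combined protocol and SAP*

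**What the plan says.** Section 15.2 sets n = 200, alpha = .05 "and power = .80 with 12 covariates in our model". The effect sized is the condition x sex x puberty interaction "within a multiple regression model controlling for the 12 covariates, all two-way interactions, and the main effects". The resulting minimum detectable f2 is 0.056 at n = 200. For imaging outcomes, assuming 40 participants are lost to movement, it is .070 at n = 160. The section closes by saying that for the two-way and main-effects models "the power will be larger than these reported values as the models will be simpler".

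Section 15.3 fixes the order of testing. The three-way interaction is tested first for every outcome, and two-way interactions follow only if it is not significant. Then: "If the two-way interactions are not significant, we will then examine main effects only models". There is also a stop rule: "If the three-way interaction is significant, we will not examine any other model". The same section applies a Benjamini-Hochberg (BH) correction without defining the family of tests. It does not say whether the two-way terms are judged one by one or as a block.

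**The concern.** The sentence in Section 15.2 compares models by complexity only. In Section 15.3 the lower-order tests are conditional on earlier results. If an interaction that is truly null reaches significance by chance, the sequence stops before the intended test, and a real lower-order effect is not identified as such. Each such gate takes away some of the power that the simpler model gains.

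This matters because Hypothesis 1 (Section 2.3) is that parental buffering wanes with puberty, so it rests on the condition and condition x puberty terms. The three-way term brings in sex, which Section 3.2 lists as a secondary exploration. The only effect with a stated detectable size is therefore not the one that carries the hypothesis. For those that do, the plan offers only the assurance of larger power.

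**Working it through.** **Inputs.** From Section 15.2: n = 200 or 160, alpha = .05, 12 covariates, f2 = .056 or .070. From Sections 5.1 and 5.2: condition has three levels (2 df) and puberty is continuous (1 df). Sex takes 1 df. Model terms are then:

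- three-way model: 12 + 4 (main effects) + 5 (two-way) + 2 (three-way) = 23
- two-way model: 12 + 4 + 5 = 21
- main-effects model: 12 + 4 = 16

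**Formula.** Noncentral F test with u = 2 numerator df, v = n − terms − 1, and noncentrality f2 × (u + v + 1).

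**Reproducing the plan's figures.** At n = 200, v = 176 and 80% power needs f2 = .0548, against the stated 0.056. At n = 160, v = 136 and it needs .0709, against the stated .070. Both agree closely.

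**Each model tested alone**

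| | n = 200, f2 = .056 | n = 160, f2 = .070 |
|---|---|---|
| three-way | v = 176, noncentrality 10.02, power .809 | v = 136, noncentrality 9.73, power .795 |
| condition x puberty, two-way model | v = 178, noncentrality 10.14, power .814 | v = 138, noncentrality 9.87, power .801 |
| condition, main-effects model | v = 183, noncentrality 10.42, power .825 | v = 143, noncentrality 10.22, power .816 |

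Simplifying the model gains 0.5 to 2 points.

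**Under the Section 15.3 sequence.** Assume the same f2 for the lower-order effect, every other effect null, and each gate at unadjusted .05. A null gate is then passed with probability .95. Treating gates as independent:

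| Named effect | Gates before the test | n = 200 | n = 160 |
|---|---|---|---|
| condition x puberty | three-way | .95 × .814 = .77 | .95 × .801 = .76 |
| condition main effect | three-way and three separate two-way tests | .95^4 × .825 = .67 | .95^4 × .816 = .66 |
| condition main effect | three-way and one joint two-way test | .95^2 × .825 = .74 | .95^2 × .816 = .74 |

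Simulation of the full regression (24,000 data sets per scenario, with and without a sex-puberty association) gave .76 to .77, .66 to .68 and .73 to .75.

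**In the plan's own metric.** The f2 needed for 80% power under the sequence at n = 200 is about .060 for condition x puberty. For the main effect it is .066 with a joint gate and .106 with separate gates. With separate gates, main-effect power cannot exceed .95^4 = .81 however large the effect.

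**Probability that any condition term is declared significant.** In the same scenarios this is .81 to .83, because a chance-significant interaction involving condition also counts.

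**With BH across outcomes.** Assume 14 outcomes (12 fMRI variables, cortisol, heart rate), simulated as independent. The gating loss then nearly vanishes, but multiplicity lowers power. It is about .33 to .78 for condition x puberty and .35 to .78 for the main effect, depending on the BH family and on how many outcomes carry the effect.

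**The case against.** The strongest reply is that the sentence speaks of models and gives simplicity as its reason, and on those terms it is right. That stands. A reader might infer an arithmetic error, or a claim that is false whatever the order of testing. The documents support neither: the shortfall comes from the Section 15.3 sequence. Also, the .80 in Section 15.2 is an input to the three-way calculation, and the reported values are effect sizes. The plan never states 80% power for the lower-order tests at f2 = .056.

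A reader might also infer that a real condition effect would often be reported as null. That does not follow. A gate that fires produces a significant interaction, and three of the four gates ahead of the main effect contain condition. Section 15.3 then examines pairwise comparisons if condition is significant in any form. What remains is a problem of interpretation: the flagged term may be a spurious interaction, which is not evidence for Hypothesis 1.

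A figure of about .62 for condition x puberty might be quoted. It requires a joint 5-df two-way test, which the plan does not specify. On the plain reading the test falls from .81 to .77, a modest loss. The larger loss, to .67, applies to a condition main effect without a condition x puberty interaction, whereas Hypothesis 1 predicts that interaction.

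Finally, these gated figures leave out the plan's BH correction. That is fair, and it limits how they may be quoted. It does not rescue the sentence, since every BH reading tried also left power below .80.

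**Conclusion.** The point holds in a limited form. Section 15.2 claims a power advantage that is true of each model tested alone and not of the planned procedure. Before BH, at n = 200 and f2 = .056, the chance of detecting the named effect is about .77 for condition x puberty and .67 to .74 for the condition main effect. At n = 160 and f2 = .070 it is about .76 and .66 to .74. The range for the main effect reflects whether the two-way gate is separate or joint.

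These figures rest on equal f2 across orders of effect, no other true effects, and gates at unadjusted .05. The documents state none of the three. The loss is in naming the correct term, not in missing condition altogether.

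**What to change.** In Section 15.2, delete the sentence, or limit it to each model tested on its own without multiplicity correction. In its place, state power for condition x puberty and for the condition main effect under the Section 15.3 sequence. For that, Section 15.3 must say whether the two-way gate is three separate tests or one joint test, and which tests form the BH family. The values .77 and .67 to .74 may be quoted only as pre-BH figures, with the assumptions above stated beside them.

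The cost is one sentence replaced, two specifications added, a short recalculation and a less favourable power statement. Neither the design nor the sample size has to change.

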### 15.3 Statistical Analysis of MRI and non-MRI Outcome Variables:

The following is a list of the analyses that we will perform on the outcome measures. They are classified as to whether they are the primary or mediational analyses. All statistical analyses will be performed in R.

The primary analyses will consist of a series of multiple regression models. For each dependent variable, variation in neural activity, cortisol response, and heart rate response, we will begin by testing the three-way interaction between social buffering condition, sex, and pubertal stage for all outcomes. If the three-way interaction is not significant, we will then examine all two-way interactions. If the two-way interactions are not significant, we will then examine main effects only models. If the three-way interaction is significant, we will not examine any other model. If condition is significant as an interaction or as a main effect, we will examine all pairwise comparisons using Tukey's Honestly Significant Difference test.

Multiplicity of testing. We will correct for multiple comparisons using the Benjamini-Hochberg (BH) correction. The BH method works by controlling the false discovery rate, and relative to the Bonferroni's correction is more powerful, while still adequately protecting against Type I error (Williams, Jones, & Tukey, 1999).

Mediational Analysis. When changes in activity of brain regions differ by condition or condition by pubertal status and we also see condition or condition by pubertal status differences for cortisol, or heart rate, then we will examine whether brain activity differences mediate the neuroendocrine or autonomic differences. This will be examined using path analysis, while controlling for covariates identified in the preliminary

covariate analysis, and will be estimated using the lavaan package in R (Rosseel, 2012).

The significance of all indirect effects will be assessed using bias-corrected 95% confidence intervals (Efron & Tibshirani, 1986), where confidence intervals that are non-overlapping with zero will be considered significant.

Power Analysis for the Mediational Analysis: To assess power to detect mediation, we performed a Monte Carlo-based power analysis using simulated data. We varied the parameter values to roughly correspond to Cohen's criteria for small, medium, and large effects. This resulted in a total of 27 conditions, which we examined at our target sample size of 200. Each condition was replicated 2000 times and we calculated empirical power, which we defined as the proportion of times out of 2000 where we rejected the null hypothesis at  $\alpha = .05$ . Given the exploratory nature of this analysis and to simplify the simulation for the power analysis, we omitted covariates and did not vary the effects for the other condition contrasts (i.e., they were always fixed to 0). Next, we fit a path model using the lavaan package in R.

Our findings suggest that in order to detect mediation, the effect of condition on the mediator must be large and the effect of the mediator on the outcome must be medium or large. In addition, if the effect of condition on the outcome is not large, but small or medium sized, then we will be underpowered and would likely conclude complete mediation, when mediation may only be partial or non-existent. Based on this power analysis, it is likely that the MDES for the moderated mediation models will need to be at least medium to large as well.

Missing data. Because we will replace participants who do not come in for session 2 after doing session 1 (which is rare in our experience), we should have 200 completed participants. Missing data, however, could arise from problems in obtaining good imaging data. Participants also often fail to fully complete questionnaires and/or refuse to provide information on household income. If there is missingness in any of the dependent or independent variables, multiple imputation will be used (Little & Rubin, 2014; Peng, Harwell, Liou, & Ehman, 2006; Schafer & Graham, 2002). Variables related to the missingness and the variables missing data will be included in the missing data model. In the event that missingness is not at random (MNAR), we will investigate the use of models for non-ignorable missing data.

**15.4 Data Integrity:** Questionnaire data will be double-entered to reduce the likelihood of errors in data entry. Biospecimen data will be assayed in labs

that have standard quality control procedures. MRI data reviewed for raw data quality and artifact detection.

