### 2.3 Study Aims:

The current study examines the neural response, as well as the cortisol hormonal response to social evaluative stress across the transition to puberty. We use a modified version of the Trier Social Stress Test (TSST) in the MRI scanner (called the Minnesota Imaging Stress Test in Children; MISTiC) to elicit social evaluative stress. In this project, we will randomly assign youth to complete this testing under one of three social buffering conditions: presence of a parent, presence of an experimenter (stranger), or no social support present (standard imaging condition).

The **long-term goal** of our research is to enrich understanding of stress regulation and its role in human development. The **overall objective** of this project is to understand normative processes in stress regulation and their neurobiological correlates as children leave childhood and become more autonomous in adolescence. The **central hypothesis** of this project is that early adolescence is a period of time when parental buffering wanes in efficacy, leaving many youth experiencing a relative dearth of relationships that can provide powerful stress buffers.

**The aim of the current study is to delineate changes in brain activation in response to social buffering by parents over the pubertal transition.**

**Hypothesis #1:** Parental social buffering will result in increased activation in brain regions associated with safety (e.g. vmPFC) and lower activation in brain regions involved in fear and pain (e.g., insula, amygdala, hypothalamus), as well as tighter coupling between the vmPFC and amygdala activity, but these relationships will wane with pubertal development.

**Hypothesis #2:** Neural activity associated with social buffering will mediate the effectiveness of physiological buffering by social partners.

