### **3.0 Study Endpoints/Events/Outcomes**

- 3.1 Primary Endpoint/Event/Outcome:  
Neural activity in vmPFC, insula, amygdala, and hypothalamus; salivary cortisol, heart rate, and respiration
- 3.2 Secondary Endpoint(s)/Event(s)/Outcome(s):  
Exploration of possible sex differences in different conditions later in puberty but not earlier in puberty.

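### Section 15.3 opens every primary analysis with condition × sex × puberty, a secondary exploration under section 3.2, and runs the Hypothesis 1 test only if that term is non-significant

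*Combined protocol and SAP*

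**What the plan says.** Section 2.3 gives the aim as to "delineate changes in brain activation in response to social buffering by parents over the pubertal transition". Hypothesis #1 predicts neural effects of parental buffering, "but these relationships will wane with pubertal development". Both describe condition × puberty; neither mentions sex. Section 3.2 lists as the secondary outcome "Exploration of possible sex differences in different conditions later in puberty but not earlier in puberty", which is the condition × sex × puberty interaction.

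Section 15.3 sets the order of the primary regressions: "we will begin by testing the three-way interaction between social buffering condition, sex, and pubertal stage for all outcomes". Two-way interactions follow if the three-way is non-significant. Then: "If the two-way interactions are not significant, we will then examine main effects only models". And: "If the three-way interaction is significant, we will not examine any other model".

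Section 15.2 computes the minimum detectable effect "for a three-way interaction between social buffering condition, sex, and pubertal stage within a multiple regression model controlling for the 12 covariates", and treats this as the most complex model of the primary analysis. For the two-way and main-effects models it says that "the power will be larger than these reported values as the models will be simpler".

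**The concern.** The test that answers the stated hypothesis is conditional on a term that the protocol elsewhere calls secondary. Three consequences follow.

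- The pooled condition × puberty test is run only when the three-way is non-significant.
- The main-effects model is reached only when the two-way interactions are also non-significant. These include sex × puberty, which contains no condition term. Section 15.3 does not say whether one significant two-way term is enough to stop, or whether the condition term of a retained two-way model is then read.
- The power statement for the simpler models takes no account of their being reached only conditionally.

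There is also an effect on Hypothesis #2. Section 15.3 starts the mediation analysis from differences by condition or by condition and pubertal status. After a significant three-way, no model giving those pooled tests is examined, so the trigger is unclear.

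**Working it through.** **Inputs from the documents.** n = 200, three conditions and continuous puberty (section 5.1). α = .05, power .80, 12 covariates, minimum detectable f² of 0.056, and 0.070 at n = 160 (section 15.2). Outcomes: 6 task and 6 connectivity measures (section 15.1) plus cortisol and heart rate (section 15.3), so 14.

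**The plan's own figure.** Predictors: 12 covariates + 4 main-effect + 5 two-way + 2 three-way terms = 23. With u = 2, v = 200 − 23 − 1 = 176 and λ = f²(u + v + 1) = 179 f², the noncentral F gives a minimum detectable f² of 0.0548; power at 0.056 is 0.809. At n = 160, v = 136, the value is 0.0709 and power at 0.070 is 0.795. The stated figures are reproduced.

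**The same calculation for condition × puberty (u = 2).** With sex × puberty as the only other interaction there are 19 predictors: f² = 0.0535 at n = 200 and 0.0688 at n = 160. With all two-way terms there are 21: 0.0541 and 0.0698. Run unconditionally, this test needs no larger effect than the plan states.

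**Simulation of the section 15.3 sequence.** Assumptions: three equal arms (the ratio is not stated), sex coded ±0.5, puberty standard normal and independent of sex, residual SD 1, effects on the parent arm, no covariates, nested F tests at .05, 6000 replicates. The documents give no expected effects, so these are assumed:

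- condition 0.5 SD, or condition × puberty 0.5 SD per SD: f² = 0.5² × (1/3 × 2/3) = 0.056, the plan's own minimum;
- puberty slopes differing by sex by 0.3: f² = 0.3² × 0.25 = 0.0225;
- three-way of 0.5 (waning differs by sex by 0.5): f² = 0.5² × 2/9 × 0.25 = 0.014.

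| Effect and scenario | Through the sequence | Direct |
|---|---|---|
| Condition × puberty, no three-way | 77.6% | 82.0% |
| Condition × puberty, three-way of 0.3 | 70.9% | 80.8% |
| Condition × puberty, three-way of 0.5 | 58.4% | 80.8% |
| Condition, no interaction, strict reading | 67.7% | 83.5% |
| Condition, slopes differ by sex by 0.3: strict (any two-way term stops) | 34.1% | 83.6% |
| Same: only two-way terms containing condition stop | about 71% | about 83% |
| Same: condition term of the retained model is read | 79.6% | 83.6% |

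The about-71% row comes from a separate run of 4000 replicates. Other repeat runs agreed with the rest to within about 2 points.

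**Hand check.** With no three-way, condition × puberty is tested in about 95% of trials: 0.95 × 0.82 = 0.78. With no interactions, the main-effects model is reached in about 0.95⁴ = 0.815: 0.815 × 0.835 = 0.68. With slopes differing by 0.3 it is reached in about 40%: 0.40 × 0.84 = 0.34.

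**With 12 covariates** and f² = 0.056 (4000 replicates): condition × puberty 77% against 82%; condition effect 67% against 83%.

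**At n = 160**, same assumed effects: condition × puberty 68.2% against 71.5%; condition with no interaction 61.0% against 75.6%.

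**With Benjamini-Hochberg at each step** (14 outcomes, effect in all): condition × puberty loses 0–2 points if the correction is applied per term. The condition effect with no interaction is 81–82% against 82%.

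**Choice of model.** If puberty slopes differ by sex by 0.5 and sex × puberty is left out, the error rate of the condition × puberty test is about 6.6%. With that term in, it is near 5% at no loss of power (82–83%).

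**The case against.** Section 15 is consistent with itself: sections 15.2 and 15.3 both treat the three-way as primary, section 15.1 names sex among the independent variables, and testing the highest-order term first is a recognised strategy. This stands. The conflict is between sections 2.3 and 3.2 on one side and 15.2 and 15.3 on the other, and the sponsor may settle it either way.

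A significant three-way is itself a result about waning. This also stands. Sex-specific slopes are still estimated, and where a three-way was truly present 85–87% of simulated trials gave some condition-related finding. What is lost is the pooled test, not all information. Whether that counts as lost power is partly a choice of estimand.

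The 34% figure needs both a real sex × puberty effect and the strictest reading. Section 15.3 provides for pairwise comparisons when condition is significant as an interaction or as a main effect, which suggests that condition terms are read where they arise. This is a fair reading, but the text does not settle it.

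Three stronger inferences are tempting and not supported:

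- *The order inflates false positives for Hypothesis 1.* It does not; the simulated error rate is 4.7%.
- *The order is costly under Benjamini-Hochberg when all three two-way terms are pooled.* Pooling does reduce condition × puberty power, but it is 62.6% with the three-way step and 62.9% without it. The reduction comes from the size of the family, which is a separate question.
- *Hypothesis 1 is left untested or badly underpowered.* With no three-way, the loss is 4–5 points before adjustment.

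**Conclusion.** The concern holds as a conflict between sections and an avoidable dependence, and should be fixed. The wording conflict is certain. The power losses rest on assumed effects, equal arms, and normal puberty independent of sex, whereas section 8.3 stratifies recruitment by pubertal stage.

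For Hypothesis 1 the cost is small unless a three-way is real. For the condition effect it runs from about 4 points to about 50, depending on an unstated reading and on whether puberty slopes differ by sex. With no interaction, the loss of about 16 points nearly disappears under Benjamini-Hochberg when every outcome carries the effect. The statement that simpler models have more power is right for tests run unconditionally, but not for condition × puberty as reached here: about 77% at f² = 0.056 with 12 covariates, against the planned 80%.

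**What to change.** 1. Reconcile sections 2.3 and 3.2 with 15.2 and 15.3 on whether condition × sex × puberty is primary. If it is, the aims and endpoints must say so.
2. Either way, delete the rule that a significant three-way stops all other models. For each outcome, always test and report condition × puberty and the condition effect at mean puberty.
3. If section 3.2 stands, make the three-way and condition × sex secondary, and show sex-specific slopes beside the pooled slope. Reconcile the trigger for the additional pubertal hormone assays in section 5.2, which is a three-way finding, with that status.
4. Preferably fit condition × puberty in a model with condition, sex, mean-centred puberty, sex × puberty and the section 15.1 covariates. State the Benjamini-Hochberg family for this test.
5. Have section 15.2 name condition × puberty as a term it covers: minimum detectable f² about 0.054 at n = 200 and about 0.07 at n = 160, no worse than stated.

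Cost: text changes only, with no new data or participants. If a three-way is real, the pooled slope averages over sexes that differ, which is why the sex-specific slopes must stand beside it.

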## 5.0 Procedures Involved

5.1 Study Design: The study design is cross-sectional. 200 target children (11- to 14-year-olds) will be randomly assigned to one of three conditions: (1) no social support (standard MRI scanning condition); (2) presence of a stranger (experimenter); or (3) presence of a parent. Outcome measures will be compared across the three social buffering conditions. Pubertal stage will be included as a continuous variable in analyses of physiological and/or brain responses.

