## **10.0 Local Number of Participants**

*10.1 Local Number of Participants to be Consented:* We plan to analyze data from at least 200 target participants. To account for attrition between sessions/replacement for incomplete data, up to 300 children may be consented/enrolled.

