Given that the MISTiC paradigm has not been used previously, it is possible that the most prominent regions of activity for this task may not match the *a priori* regions identified from the prior stress and social buffering literature. Therefore, we will also conduct an exploratory group-level analysis to identify primary regions of activation for the same socially evaluative math vs. non-evaluative math conditions (judged math vs. math alone, cluster corrected  $p < .005$ ). Because we expect that social buffering will alter the activity difference between social evaluative and non-evaluative math periods, we will use only the control condition (no social partner) to identify regions activated by this task. In the resultant group-level map, we will identify up to 4 primary regions of activation by selecting clusters that meet the cluster-corrected  $p < .005$  threshold, and then rank-ordering those regions by maximal z-statistic. Mean percent change in signal will be extracted for each participant (across all four buffering conditions) using anatomical masks derived from this analysis conducted in the control (no social partner) group. Therefore, exploratory analyses may generate up to 4 additional task-related MRI outcome variables.

Connectivity analysis: Speech preparation We are also interested in the neural correlates of anticipatory stress during the speech preparation period. However, the speech preparation period does not contain distinctive event markers needed for task-based fMRI analyses. Thus, to address the neural correlates of stress during speech preparation, we will use a seed-based connectivity approach to examine strength of functional connectivity between *a priori* seed regions of interest in the limbic system (amygdala, insula, hypothalamus) and target regions in the prefrontal

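### With three conditions, Tukey's HSD after a significant condition main effect is stricter than 5% family-wise error requires; after an interaction the same holds only for contrasts that the interaction test itself covers

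*Combined protocol and SAP*

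**What the plan says.** Section 5.1 fixes the design at three arms: children "will be randomly assigned to one of three conditions" (no partner, stranger, parent). Section 15.3 then sets a sequence for each outcome: the three-way interaction of condition, sex and pubertal stage first, the two-way interactions if that fails, and a main-effects model if those fail too. On follow-up it says: "If condition is significant as an interaction or as a main effect, we will examine all pairwise comparisons using" "Tukey's Honestly Significant Difference test". It names Benjamini-Hochberg for multiplicity without defining the family.

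The section does not say what is compared pairwise after a significant interaction: slopes on pubertal stage, conditions at chosen pubertal levels or within sex, or marginal means. It states no power for any pairwise comparison. Section 15.1, on the exploratory regions, still extracts signal "across all four buffering conditions", although the revision history records removal of the friend condition in v5.0.

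**The concern.** HSD is built to hold family-wise error over all pairs without any preceding test. Here it sits behind a 2-df test at 5%. With three means, that gate already does most of the work. HSD's larger critical value (about 2.36 against 1.97) then buys little error control after a main effect, and it costs power.

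The stake is interpretive. A significant 2-df condition test cannot say whether the parent in particular, or any company at all, changes the stress response. Only the pairwise step can. Section 15.2 also allows for a reduced imaging sample, where that power is scarcer.

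**Working it through.** **Inputs.** Three conditions (Section 5.1). N=200 from Section 10.1: "We plan to analyze data from at least 200 target participants". N=160 from Section 15.2: "even if we lose 40 of the participants to movement artifact for the imaging analyses". Also from 15.2: α=.05, "and power = .80 with 12 covariates in our model". Equal allocation, equal variances and all effect sizes below are assumptions, because the documents give none of them.

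**The plan's own figure.** Section 15.2 gives a minimum detectable f² of 0.056 for the three-way interaction (.070 at N=160). The model has 11 design terms (2+1+1 main, 2+2+1 two-way, 2 three-way), 12 covariates and an intercept. So u=2, v=200−24=176, and λ=f²(u+v+1). Solving for 80% power gives f²=0.055, and power at 0.056 is 80.9%. At N=160, v=136, f²=0.071, and power at .070 is 79.5%. The figure is reproduced. Four conditions (u=3) would give 0.063, so the power section is consistent with three.

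**Error after the main-effect test.** There are three pairwise nulls. If any two are true, all three means are equal, and the 5% F test limits the error. Otherwise at most one null is true, and a single 5% test limits the error. That is closed testing, and it needs no further adjustment. Simulation (400,000 replicates; error df 184 at N=200 and 144 at N=160) gives, at N=200:

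| Truth | F then HSD | F then unadjusted t |
|---|---|---|
| All equal | 4.5% | 5.0% |
| One condition differs | 1.9% | 4.3% to 5.0% |

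**Power after the main-effect test, parent 0.5 SD from both others.** At N=200, n=66.7 per arm, the standard error is √(2/66.7)=0.173 SD and the expected t is 0.5/0.173=2.89. Without the gate, HSD power is Φ(2.89−2.36)≈70% and unadjusted power is Φ(2.89−1.97)≈82%. The gate itself passes about 85% of the time. With the gate included:

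| N | Comparison | HSD | Unadjusted |
|---|---|---|---|
| 200 | Each parent comparison | 70% | 78% |
| 200 | Both | 56% | 71% |
| 160 | Each parent comparison | 58% | 67% |
| 160 | Both | 42% | 58% |

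**Other scenarios, N=200.** For a parent difference of 0.3, 0.4, 0.5, 0.6 and 0.8 SD, the gain per comparison is about 6, 9, 8, 5 and 1 points. Under a graded pattern (parent 0.5, stranger 0.25, none 0), parent versus none goes from 69% to 72% and parent versus stranger from 18% to 29%. The first gain is small because the gate, which passes about 73% of the time, becomes the limit.

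**Error after a condition-by-puberty interaction** (20,000 replicates, N=200, true slope difference 0.3 / 0.5 / 0.8):

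| Pairwise target | HSD | Unadjusted t |
|---|---|---|
| Differences in slopes | 1.9 / 1.9 / 1.8% | 4.3 / 4.9 / 4.8% |
| Conditions at one pubertal level where all are equal | 2.9 / 3.8 / 4.6% | 6.9 / 9.5 / 11.7% |
| Conditions at two levels (6 comparisons) | 4.2 / 5.5 / 6.4% | 9.7 / 13.5 / 16.1% |
| Truly equal marginal means | 2.0 / 4.2 / 5.0% | 4.8 / 10.0 / 12.5% |

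Only for slopes does the interaction test examine the joint null of the pairwise comparisons. For the other targets a real interaction opens the gate and leaves three or more true nulls unprotected.

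**The case against.** The strongest objection is that the sentence in 15.3 covers interactions as well as main effects, and Hypothesis 1 in Section 2.3 is that buffering wanes with pubertal development. A reader might infer that HSD can be dropped wherever that sentence applies. It cannot: the last three rows of the table show unadjusted tests well above 5%, where HSD stays near or below it. This stands, and it limits the change to two cases.

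Second, the size of the gain depends on the scenario. The 15-point gain at N=200 is for showing that the parent differs from both others. A reader might take that as the claim the study must establish, but no section says so; 15.3 asks for all pairs. Section 17.2 expects both accompanied conditions to offer some buffering, which makes a graded pattern at least as plausible. This stands.

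Third, describing the plan as adjusting twice misplaces the cause. At 0.5 SD and N=200 the gate costs HSD less than half a power point (69.9% to 69.5%), and it takes HSD's error under full equality from 5.0% to 4.5%. The loss comes from HSD's critical value. HSD also supplies simultaneous intervals. Both points stand.

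Fourth, 5% is not held over the whole sequence. With every gate at .05, at least one condition gate opens in about 18% of null trials per outcome, and Benjamini-Hochberg controls the false discovery rate. That is true under either pairwise method and does not favour HSD after a main effect.

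Finally, a reader might infer that HSD is left over from a four-condition design. The documents do not say this.

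**Conclusion.** This is an efficiency point. The present plan is conservative after a main effect, not invalid. With three conditions, unadjusted contrasts after the 2-df main-effect test, or after the 2-df interaction test for pairwise differences in that same contrast, keep family-wise error at 5% per outcome and gate.

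After the main-effect test, with equal arms and a parent 0.5 SD from both others, the gain is about 8 points per parent comparison at N=200 and 9 at N=160; for both comparisons together it is 15 and 16 points. Under the graded pattern at N=200 it is 3 points for parent versus none and 11 for parent versus stranger, which stays badly underpowered at 29%. At 0.8 SD there is almost nothing to gain. The documents do not support removing the adjustment from simple effects or marginal means after an interaction, where error can reach about 9% to 16%.

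**What to change.** In Section 15.3, state which contrasts follow each gate:

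- (a) After a significant 2-df condition effect in the main-effects model, compare the three adjusted condition means with unadjusted model-based contrasts.
- (b) After a significant 2-df interaction involving condition, compare the three pairwise differences in that same interaction contrast (for example, slopes on pubertal stage) without adjustment.
- (c) For conditions compared at chosen pubertal levels, by sex, or on marginal means after an interaction, keep HSD or another adjustment. Where several levels are examined, apply it over the whole set, since HSD run level by level reached 6.4% over two levels.

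Cite the three-group closed-testing argument for (a) and (b), and change the count of buffering conditions in Section 15.1 from four to three.

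The cost is a sentence or two before analysis and no extra recruitment. The downside is that the tests in (a) and (b) carry no simultaneous intervals, although Tukey intervals can still be reported descriptively. The argument fails if a fourth condition is restored.
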